3 OBJECTIVES AND ENDPOINTS

OBJECTIVES	ENDPOINTS	JUSTIFICATION FOR ENDPOINTS
Primary		
1. Investigate how TMS modulates EEG	1. Memory performance	1. Memory performance measures will allow us to

[figure not shown]
OBJECTIVES	ENDPOINTS	JUSTIFICATION FOR ENDPOINTS

neural measures of successful memory and the association of this modulation with behavioral performance
 
2. Examine how memory task state influences susceptibility to plasticity via TMS and determine the optimal neural state for improving memory
	
 • Accuracy: Percentage of successful (later remembered hit and correct rejection) vs unsuccessful (forgotten miss and false alarm) trials for item recognition (remember/familiar/new) and context recollection (spatial location) • d': Analysis of hits (correctly remembered as encoded) relative to false alarms (new objects labelled as encoded) for item recognition 
2. Late positive posterior ERP
 
 • ERP amplitude 500-700 ms after trial onset (encoding and retrieval) over parietal and occipital electrodes 
3. Theta/alpha power (secondary)
 
 • Power in the 4-13 Hz band 0-1000 ms after trial onset (encoding and retrieval) 
4. EEG functional connectivity (secondary)
 
 • Pearson correlation coefficients (r) between electrode time courses after trial onset (encoding and retrieval) 	
examine the effects of TMS on performance, as well as to sort successful vs unsuccessful trials for EEG analyses
 
2. The late positive posterior ERP has been previously shown to be a robust marker of successful memory performance²⁵
 
3. Task-induced changes in this frequency band have been previously associated with successful memory performance²⁶
 
4. fMRI functional connectivity modulation via network-targeted TMS has been previously associated with TMS-induced memory improvement. Whether EEG functional connectivity will be similarly altered, and the relevance to memory changes, remains unknown

Tertiary/Exploratory		
1. Search for MRI predictors of the	1. Baseline fMRI functional connectivity	It is hypothesized that TMS influences downstream targets

OBJECTIVES	ENDPOINTS	JUSTIFICATION FOR ENDPOINTS

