Memory Task: This is a test of episodic memory, including item recognition and context recollection^{30,52,53}. In the task, participants will be shown a series of objects in one of four quadrants on the screen. They will be instructed to remember the objects and where they were located, both of which will be tested later. To ensure attention and for consistency with the spatial task (see below), they will be asked to indicate by button press whether the object is primarily used outdoors (e.g., a baseball) or indoors (e.g., a television). During the encoding phase, each object will be presented for 4 seconds with 4 seconds between trials. In Experiment 1, TMS will occur during a 2 second cue before each trial and in Experiment 2, TMS will occur in the first 2 seconds of stimulus object presentation. There will be 180 encoding trials, interspersed with 180 trials of the spatial task (described below). Trial order will be randomized. The retrieval phase will occur following the end of encoding. Participants will be shown, sequentially and in randomized order, the 180 encoded objects and 180 new lure objects, for a total of 360 trials. For all trials, they will respond with whether the object was old (previously seen) or new (not previously seen) and their confidence on a scale of 1-6 (1=confident new,

Abbreviated Title: Task-dependent TMS and memory

Version Date: 11.15.22

6=confident old) as a measure of item recognition. If the object was previously seen, participants will then be asked which quadrant the item was presented in to provide a measure of context recollection. We will use two different versions of the task with different and non-overlapping sets of objects at the two test sessions and the order of versions will be counterbalanced across participants.

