Spatial Task: This is a test of spatial processing, which will serve as a control task to isolate neural markers of memory engagement, versus engagement in any task with similar visuospatial qualities. Notably, spatial processing activates a network of frontoparietal including the posterior parietal cortex regions^{54,55}, allowing it to further serve as a control to isolate hippocampal network effects of TMS from the local effects of TMS on the stimulated region. In each trial of this task, participants will be shown an arrow pointing to one corner of the screen and displayed in one of four quadrants. They will be instructed to indicate by button press whether the arrow points to the corner in which it is displayed (“match,” e.g. pointing to the upper right corner in the upper right quadrant) or a different corner (“no-match,” e.g. pointing to the upper right corner in the upper left quadrant). Accuracy of match/no-match responses will be assessed. Each arrow will be presented for 4 seconds with 4 seconds between trials. In Experiment 1, TMS will occur during a 2 second cue before each trial and in Experiment 2, TMS will occur in the first 2 seconds of stimulus presentation. There will be 180 trials, interspersed with encoding trials of the memory task. We will use two different versions of the task at the two test sessions.

TMS

The parietal target will be the region of the left posterior parietal cortex with the greatest connectivity with the left hippocampus derived from the baseline resting-state fMRI session³¹. This region was chosen because of its dense connections with the hippocampus^{56,57}. Thus, stimulation of this location can modulate function of the hippocampal-cortical network^{30-36,38}.

The control target will be vertex, a commonly used active control site which does not influence neural or behavioral activity⁵⁸.

TMS targets will be marked in the participant’s anatomical MRI volume and located with a frameless stereotaxic system. If any experiment, for any reason, fails to produce useful individual targets, a literature-based location for the parietal cortex³¹ will be used as our location of stimulation. To reduce the influence of diurnal variations in the responsiveness to neuroplasticity protocols⁵⁹, we will make every effort to test subjects during the same time of day.

[figure not shown]

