Stimulation will be delivered during the encoding phase of the behavioral task, either prior to trial onset (Experiment 1) or simultaneously with trial onset (Experiment 2; see 4.4.1 Behavioral Tasks for timing) in the form of 2-seconds of theta-burst stimulation (50 Hz pulse triplets every 200 ms; Figure 3) at 80% of the motor evoked potential threshold of the right abductor pollicis brevis muscle or 44% of maximum stimulator output, whichever is lower. This protocol has been

Abbreviated Title: Task-dependent TMS and memory

Version Date: 11.15.22

shown previously to particularly influence the hippocampal-cortical network and memory performance³⁷⁻³⁹.

Figure 3. Theta-burst stimulation.

EEG

Participants will be fitted with a 64-channel elastic EEG cap for the duration of each experiment session. Data will be recorded continuously during the study and test phases of the behavioral experiment. The EEG signal will be amplified online, filtered, and digitized continuously along with stimulus onset codes used for subsequent analysis. Independent component analysis and/or other processing techniques will be performed to isolate and remove recurring artifacts from the signal.

Single-trial waveforms will be screened for artifactual contamination. Trials will then be divided based on task type (spatial, memory encoding, accuracy of item recall (memory task) and spatial task performance. The timeseries from trials of the same type and/or accuracy will then be averaged, and the resulting waveforms will be compared across categories. For theta/alpha band analysis, we will additionally use time-frequency decomposition of the event-related averages.

MRI

We estimate a maximum of 1 hour for baseline scanning. Because scanner malfunctions and subsequent loss of data are common, we will not report these as unexpected problems.

Participants whose data are lost due to scanner malfunctions will be rescheduled, if possible.

Participants whose MRI sessions cannot be completed may enter the experiment if the MPRAGE (see below) data have been acquired. They will be rescheduled for the other scans when possible.

MRI anatomical scanning: All participants will have anatomical (MPRAGE) scans at baseline. Participants who have not had one in the past year will receive a standard clinical MRI scan of the head, which will be submitted to the Diagnostic Radiology Department CC for interpretation. Depending on the requirement for a clinical scan, this phase will take 10-30 min.

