8 STATISTICAL CONSIDERATIONS

8.1 STATISTICAL HYPOTHESIS

The primary aims are to investigate how TMS alters the EEG biomarkers of successful memory performance and how memory state-related neural changes influence plasticity of the brain. Secondary aims for this protocol will include examining the MRI connectivity predictors of TMS effects.

- Primary Objective 1: Investigate how TMS modulates EEG neural measures of successful memory and the relevance of modulation to behavioral performance
 - Hypotheses
 - a. Network-targeted parietal-TMS will improve memory performance (context recollection; Primary Endpoint 1) relative to vertex-TMS trials
 - b. Relative to vertex-TMS, parietal-TMS will also increase the Late Positive Posterior ERP (Primary Endpoint 2) and theta power (Primary Endpoint 3) during encoding on successful trials, relative to unsuccessful trials
 - c. Parietal-TMS will alter EEG functional connectivity patterns (Primary Endpoint 4) at encoding during successful trials relative to unsuccessful trials
 - d. The EEG effects will correlate with memory improvement (Correlation, Primary Endpoint 1 and 2-4)
 - e. Parietal-TMS will not influence neural activity or accuracy for spatial trials, relative to vertex-TMS and no-TMS
- Primary Objective 2: Examine how memory task state influences susceptibility to plasticity via TMS and determine the optimal neural state for improving memory
 - Hypotheses
 - a. Network-targeted parietal-TMS during memory encoding will have a larger effect on memory performance (Primary Endpoint 1), relative to pre-trial parietal-TMS and vertex-TMS during encoding
 - b. Exploratory Analyses:
 - i. Parietal-TMS during memory encoding will increase the Late Positive Posterior ERP (Primary Endpoint 2) and theta-power (Primary Endpoint 3), relative to pre-trial parietal-TMS and vertex-TMS during encoding
 - ii. Additionally, parietal-TMS will alter EEG functional connectivity patterns (Primary Endpoint 4) during later-remembered trials, relative to pre-trial parietal-TMS and vertex-TMS during encoding
 - iii. Network-targeted TMS will not influence neural activity during arithmetic trials, relative to vertex-TMS and no-TMS

- *Exploratory Objective:* Determine MRI predictors of the effects of noninvasive stimulation

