8.3.2 Analysis of the Primary Endpoints

- Primary Endpoint 1: Investigate how TMS modulates EEG neural measures of successful memory and the relevance of modulation to behavioral performance
This aim will examine behavioral and EEG neural outcome measures (Primary Endpoints 1-4). We will perform 3x3 ANOVAs on each outcome measure with the factors trial type (successful/ unsuccessful/ spatial), stimulation site (parietal/ vertex/ none), and their interaction. We will particularly focus on the main effect of stimulation site to determine

the influence of parietal-TMS on memory performance and its neural correlates, and the interaction effect to determine the task specificity of TMS effects. Thresholds for significant effects will be set at $p<0.025$ following FDR correction for multiple comparisons.

- Primary Endpoint 2: Examine how memory task state influences susceptibility to plasticity via TMS and determine the optimal neural state for improving memory
This aim will examine behavioral and EEG neural outcome measures (Primary Endpoints 1-4). We will perform 3x3x2 ANOVAs on each outcome measure with the factors trial type (successful/ unsuccessful/ spatial), stimulation site (parietal/ vertex/ none), stimulation timing (pre-trial and mid-trial) and their interaction. We will particularly focus on the interaction effect of stimulation site and timing to determine the influence of memory task-state parietal-TMS on memory performance and its neural correlates, and the three-way interaction effect to determine the task specificity of state-dependent TMS effects. Thresholds for significant effects will be set at $p<0.025$ following FDR correction for multiple comparisons.

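### For the encoding EEG outcomes, the focal site main effect in Section 8.3.2 does not test hypothesis 1b and would keep any local stimulation offset; the already planned interaction should be focal

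*Combined protocol and SAP*

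**What the plan says.** Section 3 scores the ERP endpoint as "ERP amplitude 500-700 ms after trial onset (encoding and retrieval) over parietal and occipital electrodes", and theta/alpha power as 4-13 Hz over 0-1000 ms. Section 4 (TMS) places the active coil by this rule: "The parietal target will be the region of the left posterior parietal cortex with the greatest connectivity with the left hippocampus". For the control: "The control target will be vertex, a commonly used active control site which does not influence neural or behavioral activity". On timing, "Stimulation will be delivered during the encoding phase of the behavioral task", so no pulses are given at retrieval. In Experiment 2, "TMS will occur in the first 2 seconds of stimulus object presentation"; in Experiment 1 the train comes before trial onset.

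For Objective 1, Section 8.3.2 specifies a 3x3 ANOVA of trial type (successful, unsuccessful, spatial) by site (parietal, vertex, none) and states: "We will particularly focus on the main effect of stimulation site to determine" the influence of parietal-TMS on memory and its neural correlates. The same sentence goes on to the interaction, but gives it the role of showing task specificity. For Objective 2 the focus is the site-by-timing interaction, with the three-way interaction again for task specificity.

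Hypothesis 1b (Section 8.1, and Section 4 under Primary Objective 1) is narrower. Relative to vertex-TMS, parietal-TMS should raise the ERP and theta power on successful relative to unsuccessful encoding trials. Hypothesis 1e is the negative control: "Parietal-TMS will not influence neural activity or accuracy for spatial trials, relative to vertex-TMS and no-TMS".

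**The concern.** Two things go wrong when the site main effect carries the inference for the encoding EEG outcomes.

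First, it is not the hypothesised quantity. A shift common to all trials would make it significant without any change in the successful-minus-unsuccessful difference. An effect confined to successful trials would be diluted by averaging over three trial types.

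Second, it keeps in full any offset tied to coil position. Going by the site names, the parietal coil is closer than the vertex coil to at least some of the scoring electrodes. Residual pulse artifact, scalp muscle or locally evoked activity could then differ between sites for reasons unrelated to memory. Vertex stimulation cannot subtract something local to parietal electrodes, and neither can the no-TMS level.

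At stake is whether a positive result on the late positive ERP, one of the two outcomes that share alpha in Section 8.2, could be interpreted. The same offset could make hypothesis 1e fail for a technical reason.

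**Working it through.** The plan states no figure on this point, so there is none to reproduce.

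**Timing.** Section 4 gives triplets at 50 Hz, repeated every 200 ms for 2 s: 10 triplets, 30 pulses. Assume the train starts at stimulus onset in Experiment 2, and starts 2 s before trial onset in Experiment 1.
- Experiment 2: pulses at 600, 620 and 640 ms fall inside the 500-700 ms window, and the last pulse is at 1840 ms.
- Experiment 1: the last pulse is at 1840 - 2000 = -160 ms, which is 660 ms before the window opens. Only a slow residual could remain.
- Theta/alpha: a 200 ms repeat is 1/0.2 = 5 Hz, inside the 4-13 Hz band and, in Experiment 2, inside the 0-1000 ms window.

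**What each contrast keeps.** Let an offset *a* be added to every parietal-stimulated trial type in Experiment 2.
- Site main effect: (a + a + a)/3 = a. Kept in full.
- (Successful - unsuccessful) under parietal minus the same under vertex: a - a = 0.
- (Memory - spatial) under parietal minus the same under vertex: a - a = 0.
- Site by timing: a - 0 = a. Kept, because Experiment 1 has no matching overlap.

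**Illustrative size.** The documents give no value for *a*, so a range is assumed. Take N = 32, alpha 0.025 (taken as two-sided), no true effect, and no FDR step. For a paired parietal-vertex t-test with offset d_z (in SDs of the within-person difference), noncentrality is d_z × √32 on 31 df:

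| d_z | noncentrality | false-positive rate |
|---|---|---|
| 0 | 0 | 2.5% |
| 0.15 | 0.85 | 8% |
| 0.25 | 1.41 | 19% |
| 0.5 | 2.83 | 68% |

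Now let *a* be 0.25, 0.5 or 1 cell SD, varying between people with SD a/2, with independent noise of SD 1 per cell. The parietal-vertex part of the three-trial-type main effect has noise variance 2/3:
- Main effect, Experiment 2 alone, d_z = a/√(2/3 + a²/4): 28%, 82%, 100%.
- Main effect pooled over both experiments, offset in Experiment 2 only: 8%, 28%, 82% if pooling leaves the cell SD at 1, d_z = (a/2)/√(2/3 + a²/16). With noise independent between experiments, d_z = (a/2)/√(1/3 + a²/16): 14%, 52%, 98%.
- Site by timing, d_z = a/√(4/3 + a²/4): 14%, 52%, 98%.
- The interaction contrasts of site with successful - unsuccessful, and with memory - spatial, stayed at about 2.5% in simulation throughout.

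**Variance cost.** With equal counts and independent noise σ² per cell, the main-effect difference has variance 2 × σ²/3 = 2σ²/3, and the interaction contrast 4σ². The ratio is 6. Table 1 gives 30 stimulated memory and 30 spatial trials per site and experiment. If memory splits 15/15, the ratio is (1/15 + 1/15) / [(1/15 + 1/15 + 1/30)/9] = 7.2. A 24/6 split gives (1/24 + 1/6) / [(1/24 + 1/6 + 1/30)/9] = 7.8.

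The signals differ too. If the true effect δ is confined to successful trials, the main effect sees δ/3 against SD √(2/3)σ (ratio 0.41 δ/σ). The interaction sees δ against SD 2σ (0.50 δ/σ). If stimulation shifts successful and unsuccessful trials equally, the interaction sees nothing.

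**The case against.** The plan already contains much of the protection. The site-by-trial-type interaction is planned in Section 8.3.2 and includes both contrasts that cancel an additive offset. Hypothesis 1b is already worded as successful relative to unsuccessful. Section 4 names the spatial task as the control separating network effects from local effects of stimulation. The EEG part of Objective 2 is labelled exploratory, and a three-way interaction is planned for it. Section 4 (EEG) provides for independent component analysis or other artifact removal and for single-trial screening. All of this stands, and it narrows the point to which planned test carries the inference. It does not remove the point, because Section 8.3.2 gives that role to the main effect.

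A reader might infer that the parietal-vertex encoding contrast is shown to be contaminated. The documents do not support that. They give no electrode list, coil distance or residual after cleaning, and averaging over the parietal and occipital electrodes could dilute a left-sided local signal. Direct pulse overlap is limited to Experiment 2 encoding. Nor is vertex the plan's only control.

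It is also fair to say that locally evoked activity is a real stimulation effect and of interest under Objective 1. That is a reason to keep plain encoding site comparisons, labelled for what they are.

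**Conclusion.** The point holds in a limited form. For the encoding ERP and theta/alpha power, the focal test in Section 8.3.2 does not match hypothesis 1b. It also leaves any additive site offset in the result, mainly through Experiment 2, and so does the site-by-timing test for Objective 2. The mismatch follows from the text alone. The offset is an uncontrolled risk: the 8%, 19% and 68% figures are illustrations for assumed offsets in a two-condition paired test, not estimates for this trial. The planned test has three site levels, and an FDR step would lower the rates. The retrieval ERP has no concurrent pulses and is not affected by direct overlap. Cancellation in the interaction assumes that the offset is the same across trial types.

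**What to change.** In Section 8.3.2, for encoding late positive ERP and theta/alpha power, make the already planned site-by-trial-type interaction focal. State it as one pre-specified contrast: (successful - unsuccessful) under parietal minus (successful - unsuccessful) under vertex. For the exploratory Objective 2 EEG comparison, make the already planned three-way interaction focal, for example through memory minus spatial within the same session and timing. Report the parietal-vertex difference on spatial trials as a check on local or artifact effects. Keep plain encoding site comparisons as descriptive.

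No new data are needed. The cost is precision at a fixed N of 32: about six times the variance of the three-trial-type main effect under equal counts and independent noise, and more when the 30 stimulated memory trials per cell split unevenly by success. An offset that differs by trial type would not cancel, so the spatial-trial check does not settle everything.

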Devices determined to be used on label or other exempted devices pursuant to 21CFR812.2(c):

GE Discovery MR 750 System-3T. 510k: K163331

- a. This device and associated system carries an FDA 510(k) clearance . The Sponsor has determined that the device is used in the trial in accordance with this label.

Primary Objective

Primary Objective 1: Investigate how TMS modulates EEG neural measures of successful memory and the association of this modulation with behavioral performance

- Hypotheses

Abbreviated Title: Task-dependent TMS and memory

Version Date: 11.15.22

- Network-targeted parietal-TMS will improve memory performance (context recollection; Primary Outcome Measure 1) on parietal-TMS relative to vertex-TMS trials
- Relative to vertex-TMS, parietal-TMS will also increase the Late Positive Posterior ERP (Primary Outcome Measure 2) and theta power (Secondary Outcome Measure 1) during encoding on successful trials, relative to unsuccessful trials
- The EEG effects will correlate with memory improvement (Correlation, Primary Outcome Measure 1 and Primary Outcome Measure 2/Secondary Outcome Measure 1)
- Additionally, parietal-TMS will alter EEG functional connectivity patterns (Exploratory Outcome Measure 1) at encoding during successful trials relative to unsuccessful trials
- Parietal-TMS will not influence neural activity or accuracy for spatial trials, relative to vertex-TMS and no-TMS

Primary Objective 2: Examine how memory task state influences susceptibility to plasticity via TMS and determine the optimal neural state for improving memory

- Hypotheses
 - Network-targeted parietal-TMS during memory encoding will have a larger effect on source recollection (Primary Outcome Measure 1), relative to pre-trial parietal-TMS and vertex-TMS during encoding
 - Exploratory Analyses:
 - Parietal-TMS during memory encoding will increase the Late Positive Posterior ERP (Primary Outcome Measure 2) and theta-power (Secondary Outcome Measure 1), relative to pre-trial parietal-TMS and vertex-TMS during encoding
 - Additionally, parietal-TMS will alter EEG functional connectivity patterns (Exploratory Outcome Measure 1) during later-remembered trials, relative to pre-trial parietal-TMS and vertex-TMS during encoding
 - Network-targeted TMS will not influence neural activity during arithmetic trials, relative to vertex-TMS and no-TMS

Exploratory Objective:

Search for MRI predictors of the effects of parietal TMS

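### EEG functional connectivity is defined as a sensor-level Pearson r that keeps the stimulus-locked response, so it is confounded with ERP amplitude and can move in either direction with no change in coupling

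*Combined protocol and SAP*

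**What the plan says.** Section 3 gives the whole definition of the measure: "Pearson correlation coefficients (r) between electrode time courses after trial onset (encoding and retrieval". No lag, reference, electrode pairs, end of window or source model is stated. A Pearson r of two time courses without a lag term is ordinarily a zero-lag correlation.

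The neighbouring endpoints in section 3 do have windows. The LPP is "ERP amplitude 500-700 ms after trial onset (encoding and retrieval) over parietal and occipital electrodes", and theta/alpha is "Power in the 4-13 Hz band 0-1000 ms after trial onset (encoding and retrieval".

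On processing, the EEG part of section 4 names artifact removal and then averaging: "The timeseries from trials of the same type and/or accuracy will then be averaged, and the resulting waveforms will be compared across categories". It does not say whether r is taken on averaged waveforms or on single trials, and it does not mention the evoked response or volume conduction.

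Section 8.1, Primary Objective 1, states as hypothesis b a prediction about amplitude: "Relative to vertex-TMS, parietal-TMS will also increase the Late Positive Posterior ERP (Primary Endpoint 2) and theta power (Primary Endpoint 3) during encoding". The contrast there is between successful and unsuccessful trials. Hypothesis c reads "Parietal-TMS will alter EEG functional connectivity patterns (Primary Endpoint 4) at encoding during successful trials relative to unsuccessful trials". Hypothesis d then correlates the EEG measures, connectivity included, with memory improvement. Sections 8.1 and 8.3.4 carry the same measures into correlations with MRI connectivity.

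**The concern.** Electrodes that pick up the same stimulus-locked deflection share that waveform at zero lag. The deflection therefore adds to (or, with opposite polarity, subtracts from) the covariance that r measures, and its share grows with ERP amplitude.

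Hypotheses b and c use the same successful-versus-unsuccessful encoding contrast, and both go into ANOVAs with the same stimulation-site factor (section 8.3.2). If b is true, r may move for that reason alone. Because c states only that connectivity will be altered, a rise and a fall would both be read as support.

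At stake is interpretation. Section 3 asks whether EEG connectivity changes in the way fMRI connectivity has been seen to change, and whether that matters for memory. A shift in r as defined could be the LPP result in another form, and so could its correlations with memory and with the MRI measures.

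There is a second route. If r is computed on averaged waveforms, it also depends on how many trials are averaged, and successful and unsuccessful trials will generally differ in number.

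**Working it through.** The documents give no figure for this endpoint, so there is none to reproduce. The check asks how far r moves when only ERP amplitude changes.

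**Inputs from the documents.** N = 32 (section 8.2); threshold 0.025 (section 8.3.2); 30 stimulated memory trials per site and experiment before the split by success (section 4, Table 1).

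**Assumed inputs.** LPP amplitude A = 5 µV, rising 25% to 6.25 µV; background SD σ = 10 µV; background correlation between electrodes ρ = 0.5, held fixed as the true coupling; LPP shape a Gaussian bump at 600 ms with SD 120 ms; window 0-1000 ms, borrowed from the power endpoint.

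**Formula.** With electrode gains g_i and g_j, K trials averaged (K = 1 for single trials), and V the variance over time of the unit LPP shape in the window:

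r = (g_i·g_j·A²V + ρσ²/K) / √[(g_i²A²V + σ²/K)(g_j²A²V + σ²/K)]

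For 0-1000 ms, V = 0.1223. So A²V = 25 × 0.1223 = 3.06 before and 39.06 × 0.1223 = 4.78 after the LPP gain. With K = 20, σ²/K = 5 and ρσ²/K = 2.5. For equal gains:

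- before: (3.06 + 2.5)/(3.06 + 5) = 0.690
- after: (4.78 + 2.5)/(4.78 + 5) = 0.744

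The other cases follow from the same formula:

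| Pair (g_i, g_j) | 20-trial average | Single trial |
|---|---|---|
| same polarity, equal (1, 1) | 0.690 to 0.744 | 0.515 to 0.523 |
| same polarity, half gain (1, 0.5) | 0.591 to 0.628 | 0.506 to 0.509 |
| one electrode without LPP (1, 0) | 0.394 to 0.358 | 0.493 to 0.488 |
| opposite polarity (1, -0.7) | 0.050 to -0.100 | 0.468 to 0.451 |

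**Window.** Over 500-700 ms only, V = 0.0086 (4 ms sampling), because r removes the mean and little of the bump's shape remains. The equal-gain 20-trial value then moves only from 0.521 to 0.531.

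**Trial count.** With the same 5 µV LPP and K = 10, σ²/K = 10 and r = (3.06 + 5)/(3.06 + 10) = 0.617, against 0.690 at K = 20. Nothing differs between these two cells except the number of trials.

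**Detection rate.** This simulation used 32 participants, LPP mean 5 µV with between-participant SD 2, and a paired t-test on Fisher z at 0.025, with 150 runs per setting and true coupling constant. It simplifies the planned ANOVA. The ranges are for 15 and 30 trials per cell. Fifteen corresponds to an even split of the 30 trials in one experiment; 30 requires pooling both experiments.

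| Pair, LPP gain | Averaged waveforms | Single-trial r | After subtracting the condition average |
|---|---|---|---|
| equal, 0% | 1.3% to 2.0% | 2.7% to 4.7% | 2.7% to 4.0% |
| equal, +25% | 21% to 38% | 5% | 2.0% to 2.7% |
| equal, +50% | 76% to 93% | 21% to 45% | 0.7% |
| one without LPP, +50% | 7% to 10% | 5% to 12% | 1.3% to 4.7% |
| opposite, +50% | 94% to 99% | 69% to 95% | 2.7% to 3.3% |

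The Monte Carlo standard error at 2.5% is √(0.025 × 0.975/150) = 1.3 percentage points, so the last column is compatible with nominal.

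**Second model, no true coupling.** Here the background is independent AR(1) noise with SD 10 µV and the shared deflection rises from 4 to 6 µV. For a same-polarity pair, r on 30-trial averages goes from 0.35 to 0.56, and single-trial r from 0.017 to 0.036. An opposite-polarity pair goes from about -0.35 to -0.56 on averages. After subtraction, |r| for the same-polarity pair is at most 0.003.

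**The case against.** A reader might infer that r rises whenever the ERP grows, and that the hypothesised LPP increase alone would register as a connectivity change. The documents support neither. The first needs same-polarity pairs with similar gains, and no pairs or reference are named; the table shows r falling for other pairs. The second depends on the window, the pairs, the averaged or single-trial basis and the LPP gain, none of which is given. Simulated rates run from near nominal to above 90%. The averaging sentence in section 4 concerns waveform comparison and does not say that r is taken on averages. Nor does the text put connectivity in the LPP window: it says only that r is taken after trial onset.

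The remedy also has limits. Subtraction is exact only if every trial carries the same ERP. With background SD 5 µV, assumed trial-to-trial variation in ERP amplitude (CV 0.5) leaves a residual r of 0.020 at 4 µV and 0.034 at 6 µV; with CV 1 the values are 0.056 and 0.111. A lag-based index is not needed for this bias and has an amplitude dependence of its own. In a simulation with a fixed 45-degree lag and 30 trials, raising 6 Hz amplitude from 2 to 4 µV moved the weighted phase-lag index from 0.24 to 0.43, and section 8.1 also predicts higher theta power.

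On weight, connectivity is secondary in sections 1.1 and 3 and Exploratory Outcome Measure 1 in section 4, though section 8.1 numbers it Primary Endpoint 4. Section 8.2 shares alpha only between memory performance and the LPP.

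All of this stands. It limits the direction, size and weight of the point. It does not remove the confounding, because no stated step separates r from ERP amplitude.

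**Conclusion.** The point holds as a cheap improvement. As defined, the connectivity measure includes the stimulus-locked response and is confounded with ERP amplitude. An LPP increase can move r up or down with coupling unchanged, and the undirected hypothesis would accept either.

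The effect is large for averaged waveforms over about 0-1000 ms and small for single-trial r with a modest LPP gain or for a window of 500-700 ms. These sizes rest on assumed amplitudes, noise and background correlation; the confounding itself follows from the definition. Averaged-waveform r has the further dependence on trial count.

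The analyses of memory performance and the LPP, and the sample size, are untouched. What should not be done is to read this r as evidence independent of the LPP.

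**What to change.** In section 3, redefine the measure. Compute r on single trials after subtracting each participant's condition-average waveform, with matched trial numbers per cell, over a stated window, reference and set of electrode pairs. Report the unsubtracted r only as a descriptive supplement, with a note that it is not independent of the LPP. Use the subtracted measure in the correlations with memory and MRI. As an optional sensitivity analysis, add an index insensitive to zero-lag mixing, such as the weighted phase-lag index or imaginary coherence, without making it the replacement.

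The cost is a changed definition and analysis code, with no new data or visits. The downsides are that subtraction is incomplete if ERP amplitude varies between trials, that matching discards some trials, and that a lag-based index misses true zero-lag coupling and can vary with oscillatory power.
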